#### 5.5. Dose delays, modifications or discontinuation for hematologic side effects

#### 5.5.1. Thrombosis/Embolism

Subjects who experience a deep venous thrombosis or a pulmonary embolus, transient ischemic attack or stroke, or a myocardial infarction at any time while on EPAG will discontinue drug and go off study. They will be treated for the thrombotic event as clinically-indicated.

## 5.5.2. Peripheral blood smear shows new morphological abnormalities

The presence of persistent morphologic abnormalities (red cell teardrop forms or immature blasts) or the development of significant sudden worsening of platelet or neutrophil counts while on study will require discontinuation of EPAG and performance of a bone marrow examination to assess for development of abnormal fibrosis or progression to MDS or AML.

#### 5.6. Extended access to study drug

Subjects who demonstrate response by protocol criteria at 24 weeks (± 10 days) may be consented to continue EPAG on study. This part of the study will be referred to as extended access phase. Per dosing criteria given in §5.1, patients may remain on the extended access phase as long as they maintain a response. While on extended access, participants may have drug tapered, discontinued, and/or re-started as per §5.2, 5.3 and 5.4.

## 5.7. Permitted supportive care

- Transfusion supportive care (e.g., blood and platelets) as clinically indicated.
- Iron chelation therapy (e.g. deferasirox, deferoxamine, deferiprone) ongoing at the time of enrollment will be continued, titrating and/or discontinuing according to established standards of care.
- Estrogens or combination oral contraceptives as indicated for uterine bleeding.
- Prophylactic antibiotics and antivirals as clinically indicated.
- The PI should be informed about all medications initiated after starting treatment with EPAG.

## 5.8. Non-permitted medications

- Romiplostim (N-Plate)
- IL-11 (Neumega)
- Androgens (danazol and oxymetholone) within 4 weeks prior to starting EPAG.
- Corticosteroids within 4 weeks prior to starting EPAG, except at physiologic replacement dosing for adrenal insufficiency

- Investigational or not marketed drugs without a well-known safety profile within 7 days or 5-half-lives (whichever is longer) prior to the first dose of study treatment and until eltrombopag is discontinued unless, in the opinion of the Investigator and Sponsor, the medication will not interfere with the study.
- Herbal supplements within 7 days (or 14 days if the drug is a potential enzyme inducer) or 5-half-lives (whichever is longer) prior to the first dose of study treatment until eltrombopag is discontinued, unless in opinion of the Investigator and Sponsor, the medication will not interfere with the study treatment.
- 5.9. Concurrent medications

**OATP and BCRP substrates:** In vitro studies demonstrated that eltrombopag is an inhibitor of the transporters OATP1B1 (Organic Anion Transporter Polypeptide-1B1) and BRCP (Breast Cancer Resistance Protein). Administration of eltrombopag 75 mg once daily for 5 days with a single 10 mg dose of rosuvastatin, an OATP1B1 and BCRP substrate, increased plasma rosuvastatin  $C_{\text{max}}$  by 2-fold and AUC $\infty$  by 55% on average. Interactions are also expected with other HMGCoA reductase inhibitors.

When co-administered with eltrombopag, a reduced dose of HMG-CoA reductase inhibitors should be considered, and careful monitoring should be undertaken. Concomitant administration of eltrombopag and other OATP1B1 and BCRP substrates should be undertaken with caution.

**Examples of OATP substrates:** aliskiren, ambrisentan, anacetrapib, atenolol, atrasentan, atorvastatin, bosentan, bromociptine, caspofungin, cerivastatin, celiprolol, danoprevir, empangliflozin, ezetimibe, fimasartan, fexofenadine, fluvastatin, glyburide, maraviroc, SN-38 (irinotecan metabolite), rosuvastatin, simvastatin acid, pitavastatin, pravastatin, repaglinide, rifampin, valsartan, olmesartan, telmisartan, montelukast, ticlopidine.

**Examples of BCRP substrates:** atorvastatin daunorubicin, doxorubicin, hematoporphyrin, imatinib, methotrexate, mitoxantrone, pitavastatin, rosuvastatin, SN-38, ethinyl estradiol, simvastatin, sulfasalazine, sofosbuvir, topotecan, sulfasalazine.

**Inhibitors of cytochrome p450:** *In vitro* studies demonstrate that CYP1A2 and CYP2C8 are involved in the oxidative metabolism of EPAG. Trimethoprim, gemfibrozil, ciprofloxacin, fluvoxamine and other moderate or strong inhibitors of CYPs may therefore theoretically result in enhanced activity of EPAG, however these interactions have not yet been established in clinical studies. Subjects on cyclosporine requiring prophylaxis against PCP should be given inhaled pentamidine instead of TMP/SULF. NIH patients with bone marrow failures are routinely placed on pentamidine instead of TMP/SULF for PCP prophylaxis to avoid potential marrow-suppressive effects of TMP/SULF anyway. Other CYP inhibitors can be used concomitantly but with careful attention to possible increased EPAG activity and toxicity.

Page 31 of 97

**HMG-CoA Reductase Inhibitors (statins):** Patients will be permitted to use HMG-CoA reductase (3-hydroxy-3-methyl-glutaryl-CoA) inhibitors during the study, but these drugs should be used with caution and a 50% dose reduction of the HMG-CoA reductase inhibitor is recommended, with close monitoring for safety, such as liver chemistry and signs and symptoms of myolysis, and efficacy, such as cholesterol and triglycerides (refer to individual product information for monitoring recommendations).

# 5.10. Instructions to patients

**Timing in relation to food:** Subjects will be advised to take EPAG on an empty stomach *i.e.* 1 hour before or 2 hours after a dairy-free meal containing no drugs, antacids, or products with polyvalent cations (*i.e.* aluminum, calcium, magnesium, iron, selenium and zinc) such as mineral supplements. For meals containing dairy products, patients will be advised to take EPAG at least 4 hours before or after meals.

**Timing in relation to antacids and other products containing polyvalent cations:** Because coadministration of EPAG with antacids decreased plasma AUC of EPAG by 70%, patients will be advised to take EPAG at least 4 hours before or after from antacids and other products containing polyvalent cations such as mineral supplements and dairy products.

# 5.11. Health Related Quality of Life (HRQL) Questionnaires

The relevant dimensions of HRQL being assessed in this study include (1) PROMIS Global Health, Sleep Disturbance, Applied Cognition-Abilities, Anxiety and Depression and (2) FACT- Anemia, Thrombocytopenia and Neutropenia. Patient-Reported Outcomes Measurement Information System (PROMIS®), is an initiative based on an NIH grant to establish and provide the public a free, reliable and validated commonly used measures of patient-reported outcomes. The FACT instruments are a health assessment instrument designed to measure multi-dimensional quality of life in chronic illness and its associated therapy. The different subscales selected for this study are specific for patients with diseases or treatments with hematological effects.

## 6. Clinical Evaluations

Samples will be ordered and tracked through CRIS. Should a CRIS screen not be available, the NIH form 2803-1 will be completed and will accompany the specimen and be filed in the medical record. For laboratory assessments, the following limits will be observed:

*Adult Patients:* The amount of blood that may be drawn from adult patients and volunteers (*i.e.* those persons 18 years of age or older) for research purposes shall not exceed 10.5 mL/kg or 550 mL, whichever is smaller, over any eight-week period. The amount of blood to be drawn from

volunteers and the frequency of collection shall be specified in the clinical research protocol, and exceptions to the 10.5 mL/kg or 550 mL limitations shall be approved by the IRB.

*Pediatric Patients:* For pediatric patients, no more than 5 mL/kg may be drawn for research purposes in a single day, and no more than 9.5 mL/kg may be drawn over any eight-week period.

6.1. Pre-study evaluation

Pre-study evaluations to determine eligibility and baseline status may be performed under an IRB approved protocol (for instance the screening protocol 97-H-0041, or studies such as bone marrows performed as follow-up on another NHLBI treatment trial) or as part of this protocol. Patients will be evaluated at the NIH within 12 weeks prior to signing consent. This evaluation includes a bone marrow aspiration and biopsy with cytogenetics to determine eligibility, and these results take up to two weeks to be reported. If a patient is not local, the labs listed below required to be performed within 7 days of signing consent can be performed by their home physician's outside lab, and if they confirm continued eligibility, telephone consent can be obtained. All time frames listed below are relative to the day consent is signed for this protocol. The source of the pre-study and eligibility data will be appropriately documented. The pre-study evaluations will include the following:

- Medical history and physical examination
- Concurrent medication review
- Complete blood count with differential
- Peripheral blood smear
- Reticulocyte count
- Hemoglobin F quantification by hemoglobin electrophoresis
- Erythrocyte adenosine deaminase
- DAT (direct antiglobulin test)
- Chromosomal breakage analysis (if results not available from outside/referring institute)
- Genetic testing (if results not available from outside/referring institute)
  - $\circ$   $\,$  Targeted sequencing if a family history of DBA exists and the mutation is known
  - Inherited bone marrow failure panel (NeoGenomics "Inherited bone marrow failure panel", University of Chicago "Hereditary Myeloid Malignancy and Inherited Bone Marrow Failure Panel", Cincinnati Children's Hospital "Bone Marrow Failure Syndromes Panel by next-generation sequencing", or a comparable test encompassing known DBA genes)
- Acute care panel (Na, K, Cl, CO2, Creatinine, Glucose, and Urea Nitrogen)
- Hepatic panel (Alkaline Phosphatase, ALT, AST, Total Bilirubin, and Direct Bilirubin)
- Total Protein, CK, Uric Acid, LDH
- Mineral (Phosphorus, Magnesium, Albumin, and Calcium)

- Coagulation and thrombosis screens (PT, PTT)
- Viral serologies for hepatitis A, B, C, HIV, HSV, EBV and CMV (positive serologies will have viral nucleic acid testing performed)
- Folate level
- B12 level
- Copper and zinc levels
- Iron panel (ferritin, transferrin, % saturation, total serum iron)
- Pregnancy test (blood or urine hCG in women of child bearing potential)
- Bone marrow aspiration and core biopsy, to be stained for standard morphologic analysis and quantitation of cellularity with hematoxylin and eosin, and special stains to assess reticulin and collagen, iron, primitive stem and progenitor cells via CD34 immunohistochemistry, and other lineage-specific or special stains as indicated to classify any abnormalities
- Bone marrow chromosomal analysis via standard cytogenetic techniques
- Pediatric consult for patients under 18 years of age
- Electrocardiogram (EKG)
- Review of red blood cell transfusion records for the 8 weeks prior to study entry

# 6.2. Baseline labs

Laboratory evaluations performed as part of screening may be used if obtained within 7 days prior to consent. Screening results (§6.1) may be used as baseline studies if performed within 12 weeks or as indicted below.

- Complete blood count with differential (7 days or less prior to signing consent)
- Reticulocyte count (7 days or less prior to signing consent)
- Acute care panel (Na, K, Cl, CO2, Creatinine, Glucose, and Urea Nitrogen) (7 days or less prior to signing consent)
- Hepatic panel (Alkaline Phosphatase, ALT, AST, Total Bilirubin, and Direct Bilirubin) (7 days or less prior to signing consent)
- Pregnancy test (blood or urine hCG in women of childbearing potential) (7 days or less prior to signing consent)

The below baseline testing will be obtained once patient is consented onto study:

- MRI T2\* imaging to assess liver iron concentration
- Neurodevelopmental testing for patients less than 18 years of age (recommended, but at PI's discretion)
- 24-hour urine collection to determine the total iron (at PI's discretion)
- HLA typing

- HRQL survey administration
- Immunoglobulins
- Thyroid function panel (T3, T4, and TSH)
- Research blood as detailed in §7

# 6.3. On-Study evaluations (through 6 months ± 10 days)

Subjects may be followed by their home physician or at the Clinical Center. Lab tests not done at the NIH will be faxed or securely e-mailed to the Research Nurse. The PI will review outside test results and these will be uploaded into CRIS, and all lab data will be recorded. Any progress notes from local assessments will be faxed or securely e-mailed to the research nurse and reviewed by the principal investigator.

- Complete blood counts with differential (every 2 weeks ± 10 days)
- ALT, AST, Total Bilirubin or Direct Bilirubin (every 2 weeks ± 10 days)
- Ferritin (every 2 weeks ± 10 days)
- Full iron panel (transferrin, % saturation, and total serum iron) in addition to ferritin preferred but not required

# 6.4. Landmark 3-month and 6-month evaluations

Subjects must be evaluated at the 3- and 6-month (± 14 days) time points. The 6-month time point shall be at the NIH Clinical Center. The 3-month assessment may be either at a home institution or at the NIH.

- Review of interval history and events
- Physical exam (may be omitted for 3-month evaluation if visit is not at the NIH)
- Complete blood counts with differential
- Acute care panel (Na, K, Cl, CO2, Creatinine, Glucose, and Urea Nitrogen)
- Mineral panel (Phosphorus, Magnesium, Albumin, and Calcium)
- Hepatic panel (Alkaline Phosphatase, ALT, AST, Total Bilirubin, and Direct Bilirubin)
- Other (Total Protein, CK, Uric Acid, and LDH) panel
- Reticulocyte count
- Iron panel (ferritin, transferrin, % saturation, total serum iron)
- Blood or urine pregnancy test (woman of childbearing potential only)
- Review of transfusion records (if available)

Additional assessments to be obtained at the NIH Clinical Center at the 6-month evaluation:

• Neurodevelopmental assessment for patients less than 18 years of age (if previously performed)

- Peripheral blood smear
- Hemoglobin F quantification by hemoglobin electrophoresis
- Erythrocyte adenosine deaminase
- Copper and zinc levels
- MRI T2\* imaging to assess liver iron concentration
- 24-hour urine collection to determine the total iron content at PI's discretion if indicated for iron metabolism and excretion studies
- Blood for pharmacokinetic evaluation of EPAG levels at PI's discretion. Samples drawn predose, and at 2-, 4-, 6- and 8-hour post-dose timepoints, with an optional final sample at 24 hours after dose
- Bone marrow aspiration and core biopsy, to be stained for standard morphologic analysis and quantitation of cellularity with hematoxylin and eosin, and special stains to assess reticulin and collagen, primitive stem and progenitor cells via CD34 immunohistochemistry, and other lineage-specific or special stains as indicated to classify any abnormalities
- Bone marrow chromosomal analysis via standard cytogenetic techniques
- HRQL survey administration
- Research blood as detailed in §7
- 6.5. Long term follow-up for responding patients enrolled in extended access phase

Patients fulfilling response criteria (per §8.2) at the 6-month visit will be offered participation in the extended access phase and after signing consent will be permitted to continue on EPAG for an additional 3 years. Subjects taking EPAG must be evaluated at the Clinical Center every 6 months (± 30 days) while they remain on extended access and continue periodic laboratory monitoring listed below in their home physician's office or the NIH every 4 weeks (± 10 days). Progress notes and lab tests not done in NIH will be faxed or securely e-mailed to the Research Nurse. The PI will review outside test results and these will be uploaded into CRIS and filed in the research charts, and all lab data will be recorded. The periodic laboratory monitoring will include:

- Complete blood counts with differential (every 4 weeks (± 10 days).
- Reticulocyte count every 4 weeks (± 10 days).
- ALT, AST, Total Bilirubin or Direct Bilirubin every 4 weeks (± 10 days).
- Ferritin every 4 weeks (± 10 days).
  - 6.5.1. Testing required for patients on EPAG while on extended access EPAG (up to 3 years after the 6-month visit):
    - Complete blood counts with differential (monthly ± 10 days)
    - Peripheral blood smear (every 6 months ± 30 days)
    - ALT, AST, Total Bilirubin or Direct Bilirubin) (monthly ± 10 days)

- Hepatic panel (Alkaline phosphatase, ALT, AST, Total Bilirubin and Direct Bilirubin) (every 6 months ± 30 days)
- Reticulocyte count (monthly ± 10 days)
- Hemoglobin F quantification by hemoglobin electrophoresis (every 6 months ± 30 days)
- Erythrocyte adenosine deaminase (every 12 months ± 30 days)
- Copper and zinc levels (every 12 months ± 30 days)
- Ferritin (monthly ± 10 days); full iron panel (ferritin, transferrin, % saturation, and total serum iron) preferred but not required
- Pregnancy test (blood or urine HCG in women of child bearing potential) (every 6 months ± 30 days)
- Bone marrow aspiration and core biopsy, to be stained for standard morphologic analysis and quantitation of cellularity with hematoxylin and eosin, and special stains to assess reticulin and collagen, primitive stem and progenitor cells via CD34 immunohistochemistry, and other lineage-specific or special stains as indicated to classify any abnormalities. Iron stains will be performed at the PI's discretion as indicated by clinical status or laboratory testing. (every 6 months ± 30 days)
- Bone marrow chromosomal analysis via standard cytogenetic techniques (every 6 months ± 30 days)
- HRQL survey administration (every 6 months ± 30 days)
- Iron panel (ferritin, transferrin, % saturation, total serum iron; every 6 months ± 30 days)
- MRI T2\* imaging to assess liver iron concentration (every 6 months ± 30 days during the first year of extended phase, and then if deemed necessary by the PI every 12 months ±30 days thereafter)
- 24-hour urine collection to determine the total iron content at PI's discretion if indicated for iron metabolism and excretion studies (every 6 months ± 30 days)
- Document Drug Accountability
- Review of interval history and events, and physical examination (every 6 months ± 30 days)
- Review of transfusion records (if available, every 6 months ± 30 days)
- Pediatric consult (every 6 months ± 30 days) at PI's discretion
- Research blood as detailed in §7 (every 6 months ± 30 days)
- 6.5.2. Subjects who have EPAG discontinued after tapering for a robust response during the extended access phase (see Table 3) will be followed in the following manner (up to 3 years after the 6-month visit):

- Complete blood counts with differential (monthly ± 10 days for 6 months off eltrombopag, then every 3 months ± 30 days until they reach off study criteria as per §8.6 or the study is closed)
- Ferritin (monthly ± 10 days for 6 months off eltrombopag, then every 3 months ± 30 days until they reach off study criteria as per §8.6 or the study is closed)
- Iron panel (ferritin, transferrin, % saturation, total serum iron; every 12 months ± 60 days)
- Hemoglobin F quantification by hemoglobin electrophoresis (every 12 months ± 60 days)
- MRI T2\* imaging to assess liver iron concentration (every 12 months ± 60 days if the PI deems necessary, if drug is discontinued during first year of extended phase, also obtain imaging at the 6-month visit as above in §6.5.1)
- Erythrocyte adenosine deaminase (every 12 months ± 60 days)
- Peripheral blood smear (every 12 months ± 60 days for three years)
- Bone marrow aspiration and core biopsy, to be stained for standard morphologic analysis and quantitation of cellularity with hematoxylin and eosin, and special stains to assess reticulin and collagen, primitive stem and progenitor cells via CD34 immunohistochemistry, and other lineage-specific or special stains as indicated to classify any abnormalities. (every 12 months ± 60 days for three years)
- Bone marrow chromosomal analysis via standard cytogenetic techniques (every 12 months ± 60 days for three years)
- HRQL survey administration (every 12 months ± 60 days for three years)
- 24-hour urine collection to determine the total iron content at PI's discretion if indicated for iron metabolism and excretion studies (every 12 months ± 60 days)
- Research blood as detailed in §7 (every 12 months ± 60 days)
- Review of interval history and events, and physical examination (every 12 months ± 60 days)
- Review of transfusion records (if available)

Patients who discontinue EPAG according to the response criteria who need to have EPAG reinitiated due to counts falling (see §5.3) will go back onto the evaluation schedule for patients on EPAG in the extended access phase.

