# 3. Study Design

The study is designed as a single-site, non-randomized, single-arm pilot study of the oral TPOR agonist eltrombopag (EPAG) in Diamond-Blackfan anemia (Figure 3) to test the hypothesis: *eltrombopag improves the production of red blood cells in Diamond-Blackfan anemia patients.* The primary endpoint (see §8.2) is measured at 6 months (24 weeks ± 14 days). Subjects who cannot tolerate the medication or fail to respond by the primary endpoint will be taken off study drug. Subjects who *respond* at the primary endpoint (hemoglobin increase of 1.5 g/dL or more and/or transfusion independence for the previous 8 weeks, see §8.2.1) will be able to continue EPAG on the extension part of this protocol for an additional 3 years. During the 3-year extension phase, subjects will remain on the same dose of EPAG until they reach a *robust response* (defined as hemoglobin ≥10 g/dL in the absence of transfusions for more than 8 weeks, see §8.2.1). Drug dose will then be tapered slowly to the lowest dosage that maintains a stable hemoglobin (≥ 10 g/dL) and eventually discontinued if possible (per §5.3), until they meet off study criteria (see §8.6), or the study is closed. Drug will be restarted during extension if robust response is lost (*i.e.* hemoglobin falls below 9 g/dL).

Up to 30 subjects (18 for Stage 1 & 12 for Stage 2) will be screened to accrue 25 eligible subjects for this study.

[figure not shown]

Figure 3: Study enrollment and treatment schema

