- Impaired cardiac function such as corrected QTc>450msec using Fridericia correction on the screening EKG, other clinically significant cardio-vascular disease (e.g. uncontrolled hypertension, history of labile hypertension), history of known structural abnormalities (e.g. cardiomyopathy).
- 4.2.12. Known active or uncontrolled infections not adequately responding to appropriate therapy.
  - 4.2.12.1. HIV infection is not exclusive of trial participation if the infection is effectively controlled with medications not known to interfere with eltrombopag metabolism or be metabolized by pathways known to be altered by eltrombopag (as per §4.2.6). HIV RNA viral load must be undetectable at the time of enrollment, and CD4 cell count must be  $\geq 200/\mu$ L. Patients must remain on antiretroviral therapy throughout study participation and must be periodically monitored for suppression of viral load and CD4 cell count. If drug-drug interactions between antiretroviral medications and eltrombopag are suspected, these must be addressed by a qualified clinical pharmacist or pharmacologist, and any changes to antiretroviral therapy need to be approved in consultation with an Infectious Disease and/or HIV specialist prior to enrollment.
- 4.2.13. Active malignancy or likelihood of recurrence of malignancies within 12 months
- 4.2.14. Evidence for MDS or AML as defined by WHO criteria.
- 4.2.15. Patients who have received chemotherapeutic treatment or other specific antineoplastic drugs or radiation therapy within 6 months of study entry
- 4.2.16. Female subjects who are nursing or pregnant (positive serum or urine β-human chorionic gonadotrophin (b-hCG) pregnancy test) at screening or pre-dose on Day 1.
- 4.2.17. Women of child-bearing potential, defined as all women physiologically capable of becoming pregnant, unless they are using highly effective methods of

contraception during dosing and for 30 days after the last dose of eltrompobag. Highly effective contraception methods include:

- Total abstinence (when this is in line with the preferred and usual lifestyle of the patient. Periodic abstinence (e.g., calendar, ovulation, symptothermal, post-ovulation methods) and withdrawal are not acceptable methods of contraception

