# Table 2: Criteria for the adjustment of the daily dose of eltrombopag

## 5.3. Taper of eltrombopag in the extension protocol

Once a robust blood count recovery occurs in the extension part (*i.e.* hemoglobin >10 g/dL in the absence of transfusions for more than 8 weeks), EPAG dose will be tapered according to Table 3. If hemoglobin falls to <9 g/dL or the patient again requires RBC transfusions then EPAG will be either re-initiated or the dose will be increased to the last effective strength.

Age group	Starting dose	Step 1	Step 2	Step3	Step 4
		Non-Asia	an		
≥12	150 mg	75	37.5	25	stop
6-11	75 mg	37.5	25	12.5	stop
2-5	2.5 mg/kg	1.25mg/kg	stop		
East Asian, South East Asian					
≥12	75 mg	37.5	25	12.5	stop
6-11	37.5 mg	25	12.5	stop	
2-5	1.25 mg/kg	stop			

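### No pregnancy test is required before the first re-dose when eltrombopag is restarted after taper-to-stop in the extension

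*Combined protocol and SAP*

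**What the plan says.** **Restart is a planned path.** Section 3 states: "Drug will be restarted during extension if robust response is lost", which it equates with hemoglobin below 9 g/dL. Section 5.3 adds renewed transfusion need: "If hemoglobin falls to <9 g/dL or the patient again requires RBC transfusions then EPAG will be either re-initiated". Section 5.6 says that "participants may have drug tapered, discontinued, and/or re-started as per §5.2, 5.3 and 5.4". None of these names a pregnancy check.

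**What follows a restart.** The last paragraph of 6.5.2 covers subjects who came off drug for response and who "need to have EPAG reinitiated due to counts falling (see §5.3) will go back onto the evaluation schedule for patients on EPAG". On that schedule (6.5.1) the pregnancy test is every 6 months ±30 days.

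**While off drug.** The 6.5.2 list has blood counts monthly for 6 months and then 3-monthly, and a history and examination every 12 months. It has no pregnancy test. In Table 15, both pregnancy-test cells carry footnote 3, which waives the test for robust responders who have stopped.

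**Contraception.** Exclusion 4.2.17 requires highly effective "contraception during dosing and for 30 days after the last dose of eltrompobag".

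**At first entry.** Exclusion 4.2.16 rules out a positive test "at screening or pre-dose on Day 1". Section 6.2 lists "Pregnancy test (blood or urine hCG in women of childbearing potential) (7 days or less prior to signing consent".

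**Known pregnancy.** Section 8.6 makes pregnancy, or unwillingness to use contraception, a reason to stop drug. Section 9.4 covers the reporting of pregnancies that occur on treatment.

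**The concern.** Waiving the test off drug is reasonable in itself. The difficulty is that nothing reverses the waiver before drug is given again. At first entry the protocol asks whether the woman is pregnant before it exposes her. At a restart after months off drug the same question arises, and the text does not ask it.

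Fetal exposure is at stake. The label text reproduced in 10.3.1 accepts use in pregnancy only where the mother's benefit justifies the risk to the fetus. Nobody can make that judgement about a pregnancy that nobody knows of. Section 8.6 acts on a known pregnancy but does not lead anyone to look for one.

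**Working it through.** The plan gives no figure to reproduce. The check is a reading of every pregnancy-test, contraception and restart provision, followed by interval arithmetic.

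**Step 1: is a test required before re-dose?**

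| Period | Scheduled test | Stated contraception rule |
|---|---|---|
| Entry | 4.2.16 and 6.2 | 4.2.17 |
| On drug in the extension | 6.5.1, every 6 months ±30 days | 4.2.17, during dosing |
| Off drug after taper | none in 6.5.2; waived by Table 15 footnote 3 | 4.2.17, to day 30 after the last dose |
| First re-dose | none placed | 4.2.17 applies again once dosing resumes |

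No provision puts a test before the first re-dose.

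**Step 2: how old is the last scheduled test at re-dose?** The inputs are:

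- a test at the 6-month visit (6.4), taken as extension week 0, then every 26 weeks on drug (6.5.1);
- for age 12 and over, three reduced-dose steps before stopping (Table 3) at 8 weeks each, so 3 × 8 = 24 weeks;
- taper start at extension week s, which the documents do not fix, so all values are allowed;
- relapse found at a scheduled blood count (6.5.2), with 30-day months and nominal visits.

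Drug stops at week s + 24. The age of the last test at that point is (s + 24) mod 26, which runs from 0 to 26 weeks as s varies. Adding the time off drug gives:

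| Relapse found at | Time off drug | Age of last test at re-dose |
|---|---|---|
| Third monthly count | 90/7 = 12.9 weeks | about 13–39 weeks |
| First 3-monthly count (month 9) | 270/7 = 38.6 weeks | about 39–65 weeks |

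Two checks at the third count:

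- With s = 0, the age is 24 + 12.9 = 36.9 weeks.
- With s = 2, the stop and the week-26 test coincide, so the age is 0 + 12.9 = 12.9 weeks. This low end assumes that the test is done before drug stops.

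Visit windows widen the upper ends. If the last on-drug test is already (182 + 30)/7 = 30.3 weeks old at the stop, the upper ends become 30.3 + 12.9 = about 43 weeks and 30.3 + 38.6 = about 69 weeks.

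**Step 3: when is the next test?** Two readings are open:

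- If the 6-month clock restarts at re-dose, the test falls at latest (182 + 30)/7 = 30.3 weeks afterwards.
- If the clock runs on from the last test, any test older than 30.3 weeks is already overdue at re-entry. That holds for every case at the first 3-monthly count, where the youngest test is 38.6 weeks old.

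The text does not choose between them. Neither reading places the test before the dose.

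**The case against.** The strongest reply is that the return rule in 6.5.2 already brings testing back. An overdue test falls due on re-entry, contraception applies again during dosing, and 8.6 removes anyone known to be pregnant or unwilling to use contraception. The investigator controls the restart and can order an hCG at any time. All of this is fair, and it narrows the gap. It still leaves re-dosing before testing within the rules.

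A second reply is that the protocol already accepts tests up to about 30 weeks old on drug. If stop dates are spread evenly over the 26-week cycle (an assumption), (30.3 − 12.9)/26 = 67% of restarts at the third count would have a test no older than that. This limits the added risk of early relapses. It does not help at the first 3-monthly count.

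A reader might infer four stronger points that the documents do not support:

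- **That entry sets a 7-day window before dosing.** The 6.2 window runs to consent, and 4.2.16 accepts a test at screening or on Day 1. The 7-day pre-dose test proposed here is somewhat stricter than the scheduled entry test.
- **That contraception certainly lapses for a countable number of days off drug.** This rests on 4.2.17 alone. Section 6.5.2 refers to 8.6 for off-drug subjects, and 8.6 lists unwillingness to use contraception, although the action it states is to stop drug. Whether the last dose in 4.2.17 means the last before a taper-stop or the last in the study is also open.
- **That the next test comes 30 weeks after re-dose.** That is only the latest reading.
- **That fetal harm at clinical doses is established.** Section 10.3.1 reports embryolethality and reduced fetal weight in animals at maternally toxic doses, and no teratogenicity in rats or rabbits.

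**Conclusion.** The gap is real and narrow. No section requires a pregnancy test before the first re-dose after a drug-free period, and following the waiver and the restart rule exactly permits re-exposure of an undetected pregnancy. It is a silence about restarts, not a contradiction between sections.

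The last scheduled test would be about 13–39 weeks old at the third monthly count and 39–65 weeks at the first 3-monthly count. These figures assume age 12 and over, nominal visits, any taper start date, and restart at the count that detects relapse.

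The number affected cannot be derived from the documents and is likely very small in a trial of 25. A subject must reach robust response, complete the taper, stop, relapse, be of child-bearing potential and be pregnant. Relapse during the taper leads to a dose increase with no drug-free gap. The primary analysis, sample size and error rates are untouched. The consent form was not available for this check, and wording there could narrow the gap. The change is a cheap safety improvement and worth making.

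**What to change.** Add one requirement to 5.3 and to the last paragraph of 6.5.2: within 7 days before the first re-dose after a drug-free period, women of child-bearing potential must have a negative blood or urine hCG and reconfirm contraception per 4.2.17. Amend Table 15 footnote 3 so that the off-drug waiver ends at that point.

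The cost is one sentence in each of two sections, one footnote edit, and one hCG per restart, which the home laboratory can run. The downside is a possible delay of a few days before re-dosing. No new visit, staff or invasive procedure is needed.
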